6.5.3 Cardio Flow FreedomFlowTM Orbital Circumferential Atherectomy Procedure

Subjects that meet the final angiographic eligibility criteria will have the atherectomy procedure performed according to the Cardio Flow FreedomFlowTM Orbital Circumferential Atherectomy System Instructions for Use (IFU).

Performing the Atherectomy Procedure

Interventionalist will place commercially available 0.014-inch atherectomy guidewire through appropriate size introducer sheath based on User Handle model. See IFU provided with the device for details. If this summary differs from the IFU, follow the IFU.

Caution: If the physician suspects the guidewire is placed sub-intimally, the atherectomy procedure must be aborted and alternative care performed.

1. Once the system is prepped with sterile saline, the distal tip of the User Handle driveshaft can be inserted onto the proximal end of the placed guidewire. Ensure that the guidewire clamp at the back of the User Handle is rotated to the open position to allow the guidewire to exit the User Handle.

2. While utilizing imaging technology (fluoroscopy and/or ultrasound), the physician advances the User Handle driveshaft over the guidewire through the introducer sheath and into the patient's vasculature. Continue advancement of the driveshaft and spheres until positioned proximal to the target lesion.

Caution: Verify that the guidewire distal tip is advanced as far distally in patient vasculature as feasible to ensure User Handle driveshaft does not contact the distal tip of the guidewire.

3. Once the driveshaft is in the desired location, rotate guidewire clamp clockwise and verify that the guidewire can no longer freely move.

4. Select the appropriate speed for the vessel size.

Caution: A tight lesion stenosis may require a lower speed, prior to sequential higher speed treatments. Start rotation proximal to a tight lesion stenosis.

5. Depress the blue activation button to initiate rotation and maintain selected speed.

6. Once rotation is started, slowly advance the carriage forward and backward through the target lesion.

Warning: Performing atherectomy in the presence of severe arterial spasm can result in vessel dissection or perforation. If severe spasm is observed during treatment with the FreedomFlow[™] Atherectomy System, immediately stop driveshaft rotation. If no dissections or perforations are detected, resume treatment only after the vessel spasm has spontaneously resolved or is treated pharmacologically. Prophylactic and episodic antispasm treatment may be administered as described in section 6.5.4 Procedure Medications in this protocol.

Caution: Do not leave the spheres of the driveshaft in one location for more than 5 seconds during rotation. Smooth, slow, continuous motion of the driveshaft forward and backward is recommended.

Caution: Frequent imaging evaluation, such as contrast fluoroscopy and/or ultrasound, should be utilized throughout the treatment procedure to evaluate lesion removal progress and identify potential dissections. The investigational treatment should be discontinued if a dissection is detected

7. To stop driveshaft rotation, release blue activation button.

Caution: If rotation does not cease with release of blue activation button, disconnect the User Handle.

8. To move the driveshaft to a different target lesion, rotate the guidewire clamp counterclockwise to allow the driveshaft to move independently of guidewire.

9. Rotate guidewire clamp clockwise to lock guidewire before activating the driveshaft again.

Removal of the User Handle and Driveshaft

1. Release blue activation button to stop rotation and retract driveshaft proximal to the lesion using the carriage.

2. Rotate guidewire clamp counterclockwise so that User Handle and driveshaft can move independently of guidewire.

3. Carefully remove the driveshaft from the guidewire through introducer sheath.

- 4. Turn off pump by tapping the Pump icons.
- 5. Dispose of User Handle and Tubing Set according to standard hospital practice.

Changing a Saline Infusion Bag

To change a saline infusion bag during a procedure, the operation must be paused. If the pump is turned off during a procedure, power to the User Handle will cease immediately.

- 1. Remove the User Handle and driveshaft from patient (see instructions above).
- 2. Turn off pump by tapping the Pump icons .

3. Disconnect current saline infusion bag from IV spike on the Tubing Set and hold the spike upward to prevent the introduction of air.

4. Without touching the sterile IV spike tip, insert a new saline infusion bag onto the IV spike and rehang on the IV pole.

5. Repeat a complete flush cycle of the User Handle and driveshaft.

6.5.4 Procedure Medications

Warning: Performing atherectomy in the presence of severe arterial spasm can result in vessel dissection or perforation. If severe spasm is observed during treatment with the FreedomFlowTM Atherectomy System, immediately stop driveshaft rotation.

Anti-coagulation medication and loading dose of anti-platelet medications will be given prior to the atherectomy procedure per investigational site atherectomy standard procedure. Antispasmodic medications such as nitroglycerine (200 μ g intra-arterial (IA) bolus; up to 3000 μ g per subject) or papaverine (300 μ g IA bolus) may be administered. To avoid frequent IA bolus injections, the following solution (500 ml normal saline with 3000 units heparin, 3000 μ g nitroglycerin and 2.5mg Cardizem) can be infused intra-arterially at a rate of 6 to 7 mL/min. All medications administered for this study should be recorded in the subject's medical record.

During the procedure, any device malfunction and device/procedure related adverse events, including anaphylaxis to medications or device components will be monitored and recorded.

6.6 POST PROCEDURE TO DISCHARGE

The following assessments will be performed within 12-24 hours post procedure or prior to hospital discharge, whichever occurs first:

- Physical Exam and Vital Signs
- Adverse Events assessment

6.7 30 DAYS FOLLOW-UP (± 7 DAYS)

Subjects will return for a follow-up visit at 30 days and the following assessments will be performed:

- Physical Exam and Vital Signs
- Rutherford Classification
- ABI and/or TBI
- Duplex ultrasound of treated lesion per Vascular Ultrasound Core Laboratory protocol
- Angiogram performed only if clinical symptoms requiring intervention during follow-up for TVR or TLR
- VascuQoL Questionnaire
- Adverse Events assessment

6.8 6 MONTHS FOLLOW-UP (± 14 DAYS)

Subjects will return for a follow-up visit at 6 months and the following assessments will be performed:

- Physical Exam and Vital Signs
- Rutherford Classification
- ABI and/or TBI
- Duplex ultrasound of treated lesion per Vascular Ultrasound Core Laboratory protocol
- Angiogram performed only if clinical symptoms requiring intervention during follow-up for TVR or TLR
- VascuQoL Questionnaire
- Adverse Events assessment

Table 6-1: Schedule of Events

Assessment	Screening / Baseline	Procedure	Discharge	30 Days (±7 days)	6 months (±14 days)
Informed Consent	Х				
Medical History	Х				
Physical Exam	Х		Х	Х	Х
Laboratory Assessments	Х	Х			

Urine Pregnancy Test if female	Х				
Rutherford Classification	Х			Х	Х
ABI	Х			Х	Х
VascuQoL Questionnaire	Х			Х	Х
Angiography	X ^a	Х		Xb	X ^b
Duplex Ultrasound	X ^c			Х	Х
Medications	Х		Х	Х	Х
Adverse Events	Х	Х	Х	Х	Х

^a Baseline angiography will be performed at the beginning of index procedure.

^b Angiography will be performed at the follow-up visits for verification of restenosis of the treated lesion or vessel site(s) only if the subject has clinical symptoms requiring intervention.

^c if available

6.9 UNPLANNED FOLLOW-UP

Subjects returning for unscheduled visits complaining of new signs and/or symptoms will be documented as an unplanned follow-up and, at the investigators' discretion perform diagnostic evaluations. The reason should be reported as an adverse event if applicable.

6.10 SUBJECT EARLY DISCONTINUATION / WITHDRAWAL AND REPLACEMENT OF SUBJECTS

All subjects are informed of their right to withdraw from the clinical study at any time. Additionally, the investigator may prematurely discontinue any subject's participation in the study if the investigator feels that the subject can no longer fully comply with the requirements of the study or if any of the study procedures are deemed potentially harmful to the subject. However, it is anticipated that such withdrawals will be infrequent to ensure the integrity of the study. The reason for early discontinuation will be documented in the source documents and case report forms.

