6.11 LOST TO FOLLOW-UP

Every attempt will be made to have all subjects complete the follow-up visit schedule. A subject will not be considered lost to follow-up unless efforts to obtain compliance are unsuccessful. At a minimum, the effort to obtain follow-up information will include three attempts to make contact

⁰¹⁰⁻⁰⁵⁵ Protocol Version F

via telephone and if unsuccessful, then a certified letter from the investigator will be sent to the subject's last known address.

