In order to adequately power for both primary effectiveness and primary safety hypotheses, we require a sample size of 102 mITT subjects who complete 30 days follow-up. The dropout rate

of mITT subjects is assumed to be 10 %. The final sample size for the study will be 112 subjects.

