12.9 PROTOCOL DEVIATIONS / VIOLATIONS AND MEDICAL EMERGENCIES

A protocol deviation or violation is a failure to comply with the requirements of the clinical study as specified in the protocol. Examples of protocol deviations include late visits, missed visits, required follow-up testing not completed. An example of a major protocol violation includes enrollment of a study subject who fails to meet inclusion/exclusion criteria as specified in the protocol. Each investigator shall conduct this clinical study in accordance with the study protocol and any conditions required by the reviewing IRB.

Deviations/violations from clinical protocol requirements will be reviewed and evaluated on an ongoing basis and, as necessary, appropriate corrective actions put into place. See Table 12-1: Reports Required from Investigators to Sponsor for reporting timelines for emergency deviation.

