## 6.5.2 Subject Disposition

Subject accountability and study discontinuation will be summarized for the ITT set. Subject accountability at each protocol required visit will be summarized as the number of subjects with complete visits, missed visits, or study discontinuations prior to the visit.

All subjects who do not complete the study will be tabulated by reason for discontinuation. Additional variables summarized may include total study duration, study completion status, and the primary reason for study discontinuation.

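### Protocol 6.10 lets the investigator end a treated subject's participation without requiring that day-30 MAE and vital status still be sought, and the SAP then counts such a subject as a safety success

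*Protocol*

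**What the plan says.** Protocol 6.10 gives two grounds for investigator-initiated discontinuation. The first is that "the investigator may prematurely discontinue any subject's participation in the study if the investigator feels that the subject can no longer fully comply" with the study's requirements. The second applies "if any of the study procedures are deemed potentially harmful to the subject". What ends is participation in the study as a whole. The section expects withdrawals to be infrequent, and its only recording duty is this: "The reason for early discontinuation will be documented in the source documents and case report forms".

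Protocol 6.11 opens with a general aim: "Every attempt will be made to have all subjects complete the follow-up visit schedule". It continues: "A subject will not be considered lost to follow-up unless efforts to obtain compliance are unsuccessful". The minimum effort is three telephone attempts and then a certified letter. These steps are written for subjects who are about to be classed as lost.

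Protocol 12.9 handles ordinary non-compliance as a deviation: "Examples of protocol deviations include late visits, missed visits, required follow-up testing not completed".

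SAP 6.5.2 tabulates disposition at each visit as "the number of subjects with complete visits, missed visits, or study discontinuations prior to the visit", so a discontinuation is a separate category from a missed visit.

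SAP 6.2.2 computes the primary safety proportion over all mITT subjects. Those who leave before day 30 without an event are taken to have had none.

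**The concern.** The device is used once, at the index procedure. After that, participation consists of follow-up: examination, ABI or TBI, duplex, Rutherford class, questionnaire and adverse event assessment (Protocol 6.7 and 6.8). If a duplex scan or a site visit becomes impractical or unsuitable, it can be dropped while MAE status is still obtained by telephone or from records. Section 6.10 does not provide for that middle course.

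A subject who can no longer comply, or for whom a procedure is thought harmful, may well be at higher risk of an MAE before day 30. If the site stops looking after removal, a later event goes unrecorded and SAP 6.2.2 enters the subject as a success. The error then runs in the device's favour on one of the two endpoints that decide the trial. Later analysis cannot restore outcomes that nobody collected.

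**Working it through.** **Inputs.** Performance goal 85%, assumed rate 95%, exact one-sided test at 0.025, 102 mITT subjects required, 10% dropout, 112 enrolled (Protocol 8.1, SAP 4). Early dropouts without an event are scored event-free (SAP 6.2.2). The number removed under 6.10, m, is not in the documents and is varied.

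**Step 1: the plan's own figure.** With n = 102 the exact test allows at most 8 subjects with an MAE.
- Type I error: P(Bin(102, 0.15) ≤ 8) = 0.0231.
- Power: P(Bin(102, 0.05) ≤ 8) = 0.930.

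The stated 102 subjects for at least 90% power is reproduced. Inflating by 10% gives 102 × 1.10 = 112.2, which matches the stated 112.

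**Step 2: the rule at n = 112.** The Clopper-Pearson lower bound is 85.3% for 103/112 (pass) and 84.2% for 102/112 (fail). At most 9 failures are allowed. With complete day-30 status:
- Type I error: P(Bin(112, 0.15) ≤ 9) = 0.0206.
- Power: P(Bin(112, 0.05) ≤ 9) = 0.946.

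**Step 3: m subjects removed, later events unseen.** Let f be the share of a removed subject's 15% risk that falls after removal and is therefore missed. Recorded failures are then Bin(112 − m, 0.15) + Bin(m, 0.15 × (1 − f)), and the type I error is the probability that this sum is at most 9.

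| m removed | f = 0.5 | f = 1 |
|---|---|---|
| 0 | 0.0206 | 0.0206 |
| 3 | 0.0235 | 0.0266 |
| 5 | 0.0256 | 0.0314 |
| 11 | 0.0330 | 0.0510 |

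The row m = 11 is an outer case only: 0.10 × 112 = 11.2, so it takes the whole planned dropout as removed by this route. With f = 1 the nominal 0.025 is first exceeded at m = 3 (m = 2 gives 0.0244). With f = 0.5 it is first exceeded at m = 5 (m = 4 gives 0.0245).

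**Step 4: the same gap under the worst-case analysis of SAP 6.2.4.** If all m are counted as events, power at a true 95% is P(Bin(112 − m, 0.05) ≤ 9 − m). That is 0.946 at m = 0, 0.696 at m = 3 and 0.376 at m = 5. Missing outcomes therefore also cost the sponsor, because a safe device would look fragile in that analysis.

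**The case against.** Several points on the other side stand.

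- **A reader might infer that data collection stops on discontinuation.** Section 6.10 does not say so; it is silent. Protocol 6.11 states a general aim of complete follow-up for all subjects, and Protocol 11.4 requires ongoing adverse events to be followed until resolved or stable. The gap is a missing requirement, not an instruction to stop.
- **A reader might infer that 6.10 contradicts 6.11 and 12.9.** It does not. Section 6.11 deals with subjects who cannot be reached and 12.9 with deviations by subjects who remain in the study. Both can operate beside 6.10. They simply do not cover a subject whom the investigator has discontinued.
- **Much of the composite is seen early.** Dissection and perforation are confirmed by angiography, which Protocol 6.5.1 requires after atherectomy, after adjunctive treatment and at the end of the procedure. An adverse event assessment follows within 12–24 hours or before discharge (Protocol 6.6). Hospital admissions count as serious adverse events (Protocol 11.1), and these and deaths are reportable under Table 12-1, so events known while the subject still participates should be captured.
- **Comparing about 11 planned dropouts with 9 allowed failures proves little.** The 10% is an all-cause allowance for sample size. The documents do not say what share would come from 6.10, and the comparison bites only if nearly every unknown outcome is an event.
- **Analyses of missing data are planned.** Protocol 8.3 includes a tipping-point analysis, and SAP 6.2.4 adds complete-case and worst-case analyses if missing data are a serious concern. They would show fragility, though they cannot supply the missing outcomes.

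These points limit the size of the problem. None of them supplies a rule that day-30 status be sought after an investigator-initiated discontinuation.

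**Conclusion.** The point holds as a gap in required follow-up. Protocol 6.10 lets an investigator take a treated subject out of the study on a judgement about compliance or about harm from a study procedure. No section then requires MAE or vital status at day 30, and SAP 6.2.2 turns the unknown outcome into a success. The direction of any bias favours the device.

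The size is unknown and could be small. For 3 to 5 removals, type I error moves from 0.0206 to somewhere between 0.0235 and 0.0314. This rests on three assumptions: the number removed; that removed subjects carry the same 15% risk as the rest; and that half to all of that risk falls after removal and goes unseen. Inflation is less if most events occur at the procedure, and more if removed subjects are at higher risk than average. The change is still worth making, because it is cheap and protects a primary endpoint that goes into the 510(k) submission.

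**What to change.** In Protocol 6.10, separate stopping a study visit or test from leaving follow-up. For any subject in whom the device was attempted, state that:

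- MAE and vital status are obtained at day 30 and at 6 months by telephone, from the referring physician or from medical records, unless the subject withdraws consent for contact or record access;
- if that consent is withdrawn, MAE status up to the date of withdrawal is recorded.

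Add the same record check as the last step in 6.11, after the certified letter. Non-compliance need not be deleted as a ground in 6.10 once this follow-up is required.

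The cost is one protocol paragraph, one added step in 6.11, and a few calls and record requests by existing site staff. The subject's right to withdraw is unaffected.

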6.11 LOST TO FOLLOW-UP

Every attempt will be made to have all subjects complete the follow-up visit schedule. A subject will not be considered lost to follow-up unless efforts to obtain compliance are unsuccessful. At a minimum, the effort to obtain follow-up information will include three attempts to make contact

⁰¹⁰⁻⁰⁵⁵ Protocol Version F

via telephone and if unsuccessful, then a certified letter from the investigator will be sent to the subject's last known address.

7 BENEFIT / RISK ANALYSIS

7.1 **BENEFITS**

Participation in this study is voluntary. There will be no direct benefits of participating in this study. Information gathered from this study will help confirm the safety and efficacy of the device in treating de novo, severely calcified peripheral lesions.

7.2 RISKS

The risks of the investigational procedure to subjects is similar to that of other Atherectomy procedures.

Possible risks associated with the Cardio Flow FreedomFlowTM Orbital Circumferential Atherectomy System that may occur and/or require intervention include, but are not limited to:

- Allergic reaction to medication/media/device components
- Amputation
- Anemia
- Aneurysm
- Bleeding complications which may require transfusion
- Cerebrovascular accident (CVA)
- Death
- Distal embolization
- Device embolization
- Entry site complications including hematoma
- Hemolysis
- Hypotension/hypertension
- Infection
- Myocardial infarction
- Pain
- Pseudoaneurysm
- Restenosis of treated segment that may require revascularization
- Renal insufficiency/failure
- Slow flow or no reflow phenomenon
- Dissection

⁰¹⁰⁻⁰⁵⁵ Protocol Version F

- Perforation
- Thrombus
- Vessel closure, abrupt
- Vessel injury, including dissection and perforation that may require surgical repair
- Vessel spasm
- Vessel occlusion

7.3 MINIMIZATION OF RISK AND MONITORING PROCEDURE

Cardio Flow, Inc. has attempted to mitigate risks as much as possible through product design, testing, and through careful labeling and instructions for use.

8 STATISTICAL METHODS AND ANALYSIS

The study is designed as a prospective, multi-center, nonrandomized single arm study to evaluate the safety and effectiveness of the Cardio Flow FreedomFlowTM Orbital Circumferential Atherectomy System for atherosclerotic plaque removal and vessel compliance modification in *de novo* native target lesions in the peripheral vasculature of the lower extremities.

8.1 DETERMINATION OF SAMPLE SIZE

The sample size is calculated to simultaneously power for the primary effectiveness and primary safety endpoints by comparison to the pre-specified Performance Goal (PG).

Primary Effectiveness Endpoint

Sample size estimates were calculated for the primary effectiveness outcome by comparing the technical success rate to the pre-specified performance goal of 86% The performance goal of 86% was derived using a random effect meta-analysis based on the technical success rates that were obtained from the results of recent atherectomy studies (See Table 8-1 below) and an allowed 10% margin. The underlying technical success rate was assumed 96%.

The hypotheses are:

H₀: technical success rate $\leq 86\%$

Ha: technical success rate > 86%

Under an exact, one-sided test for a single binomial proportion, at the 0.025 significance level, a sample size of 101 mITT subjects will be required to provide 90% power to meet this technical success endpoint.

⁰¹⁰⁻⁰⁵⁵ Protocol Version F

Study	N	Success	Technical Success Rate	
Davis et al 2017 ²⁵ /IFU (Phoenix) ²⁶	123	117	95.1%	
Roberts et al 2014 ²⁷ (SilverHawk)	131	121	92.4%	
Zeller et al 2009 ²⁸ (Pathway)	210	208	99.1%	
Weighted Average (95% CI)	96% (90%, 99%)			

Table 8-1: Technical Success Rates

Primary Safety Endpoint

Literature review and a random effect meta-analysis showed a 95% freedom from MAE at 30 days. The pre-specified performance goal for the primary safety endpoint is 85% and was derived using a random effect meta-analysis based on the Freedom of MAE rates from recent atherectomy studies and an allowed 10% margin.

The hypotheses are:

H₀: Freedom from MAE at 30 days $\leq 85\%$

Ha: Freedom from MAE at 30 days > 85%

Under an exact, one-sided test for a single binomial proportion at the 0.025 significance level, a sample size of 102 mITT subjects will be required to provide at least 90% power to meet this primary safety endpoint.

Study	Ν	MAE Event	Freedom from MAE Rate	
Davis et al 2017 ²⁵ /IFU (Phoenix) ²⁶	105	6	94.29%	
Roberts et al 2014 ²⁷ (SilverHawk)	131	9	93.13%	
Safian et al 2009 ²⁹ (Diamondback)	124	4	96.77%	
NCT01937351 ³⁰ (Pantheris)	130	9	93.08%	
Dipple et al 2015 ³¹ (Turbo-Power Laser/PTA)	167	9	94.61%	
Zeller et al 2017 ³² (DA+DCB)	48	1	97.92%	
Zeller et al 2009 ²⁸ (Pathway)	172	2	98.84%	
Weighted Average (95% CI)	95% (93%, 97%)			

Table 8-2: Freedom from MAE Rates

Overall Sample Size

In order to adequately power for both primary effectiveness and primary safety hypotheses, we require a sample size of 102 mITT subjects who complete 30 days follow-up. The dropout rate

of mITT subjects is assumed to be 10 %. The final sample size for the study will be 112 subjects.

